4. STUDY POPULATION

4.1 Population (base)

The research population are patients (n= ~2000) who underwent kidney transplantation in Erasmus MC between Jan 2010 and December 2020. Based on the pre-transplant existence of aortoiliac stenosis, all patients will be divided into non-stenosis group (n=~1800) and stenosis group (n=~120).

4.2 Inclusion criteria

Patients who underwent kidney transplantation in Erasmus MC between Jan 2010 and December 2020 will be included in the study.

4.3 Exclusion criteria

Patients under 18 years old and who underwent combined kidney and liver transplantation will be excluded from the study.

4.4 Sample size calculation

Sample size calculation is performed by G*Power for future use of t test. Both the accepted false positive and negative rate is 5%. The results indicate the sample size should be at least 105 in each group to reach a reliable answer, which is feasible based on the current patient population.

The protocol of power analyses are as follows:

Analysis: A priori: Compute required sample size

Input:	Tail(s)	=	Two
	Effect size d	=	0,5
	α err prob	=	0,05
	Power (1- β err prob)	=	0,95
	Allocation ratio N2/N1	=	1
Output:	Noncentrality parameter δ	=	3,6228442
	Critical t	=	1,9714347
	Df	=	208
	Sample size group 1	=	105
	Sample size group 2	=	105
	Total sample size	=	210
	Actual power	=	0,9501287

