8. METHODS

8.1 Study parameters/endpoints

8.1.1 Main study parameter/endpoint

Primary outcome measures are patient survival and death-censored graft survival.

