8.1.2 Secondary study parameters/endpoints (if applicable)

Secondary outcome measures are renal function (such as eGFR) and vascular complications.

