10. STATISTICAL ANALYSIS

Patient survival, death-censored graft survival and eGFR will be reported as mean \pm standard deviation (SD) if normally distributed or median with interquartile range (IQR) if data is skewed. Categorical variables such as the incidence rate of vascular complications will be described as numbers and percentages. Continuous variables will be compared using student's t-test or Mann–Whitney U test. Categorical variables will be compared using χ^2 test or Fisher's exact test. Kaplan-Meier curves and log-rank test will be used to compare patient and graft survival. The data will be analyzed in SPSS. A p-value of < 0.05 is considered statistically significant.

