10.1 Primary study parameter(s)

Patient survival is defined as the time from transplantation to death or the last follow-up. Death-censored graft survival is defined as the time from transplantation to graft failure or the last follow-up with a functioning graft, with censoring death with a functioning graft.

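### The only power statement (95%, 105 per group) is for a t test with no named endpoint, while both primary endpoints are censored times compared by log-rank

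*Combined protocol and SAP*

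**What the plan says.** Section 4.4 contains the only sample size or power calculation: "Sample size calculation is performed by G*Power for future use of t test". Its inputs are a two-sided test, d = 0.5, alpha 0.05, power 0.95 and 1:1 allocation. It says "Both the accepted false positive and negative rate is 5" per cent, and concludes that "The results indicate the sample size should be at least 105 in each group to reach a reliable answer". It gives no endpoint, standard deviation, hazard ratio, event rate or length of follow-up.

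Section 8.1.1 states: "Primary outcome measures are patient survival and death-censored graft survival". Section 10.1 makes both of them censored times. For the first, "Patient survival is defined as the time from transplantation to death or the last follow-up". The second runs to graft failure and is censored at last contact with a working graft or at death with one. Section 10 then says "Kaplan-Meier curves and log-rank test will be used to compare patient and graft survival".

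Two other places bear on where the t test came from. Section 10 also says "Patient survival, death-censored graft survival and eGFR will be reported as mean" and SD, or median and IQR. Section 8.1.2 places eGFR among the secondary outcomes: "Secondary outcome measures are renal function (such as eGFR) and vascular complications".

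**The concern.** The study is sized for one test and its primary question is answered by another. A t test's power follows from the number of patients and the standardised mean difference. A log-rank test's power follows from the number of deaths or graft failures, the hazard ratio and the split between groups. A calculation of the first kind says nothing about the second unless events and effect are specified, and they are not.

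What is at stake is the reading of a null result. Section 3 makes the survival comparison the basis for judging whether stenosis affects survival, and section 1 argues for wider selection of transplant candidates. If the log-rank test is not significant, the only false negative rate on record is 5%, and it belongs to a different test. A reader could take absence of significance as good evidence of no effect when the plan gives no basis for saying which effects would have been missed.

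**Working it through.** **1. The plan's own figure.** With n = 105 per group and d = 0.5 (section 4.4), the noncentrality is 0.5 × √(105/2) = 3.6228, df = 208 and critical t = 1.9714. The noncentral t distribution gives power 0.9501, and n = 104 gives 0.9483. The figure reproduces exactly and 105 is the minimum for that t test.

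**2. Log-rank events, with no event rate assumed.** For a two-sided 5% test with 95% power, where p is the share of patients in one group:

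D = (1.960 + 1.645)² / [p(1 − p)(ln HR)²], with (1.960 + 1.645)² = 12.995.

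- 1:1, HR 1.5: 12.995 / (0.25 × 0.1644) = 316.2, so 317 events. Section 4.4 has 210 patients.
- 1:1, HR 2.0: 108.2, so 109 events.
- 1:2 (120 vs 240, assumed), HR 1.5: 355.7, so 356 of 360 patients.
- 1:3 (120 vs 360, assumed), HR 1.5: 421.6, so 422 of 480 patients.

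Ceiling at 1:1: if all 210 patients had the event, power at HR 1.5 would be Φ(0.4055 × √210 / 2 − 1.960) = Φ(0.978) = 83.6%. The smallest HR with 95% power would be exp(2 × 3.605 / √210) = 1.64. With 120 pairs (240 events) these become 88.1% and 1.59.

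**3. Patient survival with censoring (illustration).** Assumptions:

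- Control 5-year survival of 75.7% or 84.6%. These are the US registry figures for deceased- and living-donor transplants in section 1; the 5-year horizon is inferred. A third value, 60%, is assumed.
- Exponential survival, transplants spread evenly over 2010–2020 and a cut-off at the end of 2021, so follow-up is uniform from 1 to 12 years.
- The two groups are treated as independent, although section 3 plans propensity score matching.

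With λ = −ln(S₅)/5, the probability of an observed death is 1 − (e^(−λ) − e^(−12λ))/(11λ). SE(ln HR) = √(1/d₁ + 1/d₀), and power = Φ(ln HR / SE − 1.960).

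Worked case (105 per group, 75.7%, HR 1.5): λ = 0.0557 in controls gives probability 0.293, or 30.7 deaths. The stenosis group has probability 0.398, or 41.8 deaths. SE = √(1/41.8 + 1/30.7) = 0.238, and power = Φ(0.4055/0.2376 − 1.960) = Φ(−0.253) = 40%.

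Results for control survival 75.7% / 84.6% / 60%:

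| Groups | Power, HR 1.5 | Power, HR 2.0 |
|---|---|---|
| 105 vs 105 | 40% / 28% / 56% | 86% / 70% / 96% |
| 120 vs 240 | 58% / 42% / 76% | 97% / 90% / over 99% |
| 120 vs 360 | 64% / 48% / 81% | 99% / 94% / over 99% |

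The HR detectable with 95% power is 2.25 / 2.65 / 1.96 at 105 per group and 1.82 / 2.04 / 1.66 at 120 vs 360. Moving the cut-off between mid-2021 and the end of 2023 shifts the HR 1.5 power at 105 per group over 38–48% / 27–35% / 53–64%. A simulated log-rank test (4,000 runs) agrees closely: 0.41 / 0.29 / 0.58 at HR 1.5 with 105 per group.

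**4. Death-censored graft failure.** The documents give no rate. Assume 5% to 20% failure at 5 years and add death as a censoring hazard of −ln(0.757)/5 in both groups. The HR detectable with 95% power then runs from about 5.5 (5% failure) down to 2.6 (20%) at 105 per group, and from 3.3 down to 2.0 at 120 vs 360.

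**The case against.** The strongest reply is that the cohort is retrospective and takes every eligible transplant. The stenosis group is whatever exists, about 120 patients, so no recruitment target, stopping decision or patient burden hangs on section 4.4. That stands, and it limits the consequence to interpretation. It does not make the statement right: the sponsor chose to state a power and to declare the size feasible on the strength of it.

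Second, section 4.4 says that it concerns a t test and never attaches 95% to the log-rank comparison. That is true. But it names no endpoint, its conclusion is unqualified, and no other power statement exists. The mean and SD reporting in section 10 may explain the choice but does not rescue it, since the mean of censored times is not what the log-rank test compares.

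Third, the magnitudes rest on assumed hazard ratios, survival, cut-off and matching ratio. That also stands. The 72% miss rate is the least favourable corner: living-donor survival for all controls and only 105 per group. With 120 pairs the same input gives a 68% miss rate, and with 1:3 matching 52%. At HR 2.0 several scenarios exceed 95% power. The ceiling in which every patient has the event is a bound, not a realistic scenario.

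Finally, nothing in section 4.4 links d = 0.5 to eGFR, so simply relabelling the calculation would need its own justification. That is fair and is taken up in the fix.

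**Conclusion.** The concern holds. The stated 95% power is correct for an unnamed t-test comparison and is not established for patient survival or death-censored graft survival.

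The finding itself needs no outside assumption: the tests differ, and the plan supplies neither events nor a hazard ratio. One part of its size depends only on the 1:1 design and the standard log-rank formula: with 210 patients, 95% power cannot be reached for any hazard ratio between 1 and 1.5 (or, mirrored, 0.67 to 1), whatever the event rate. The remaining figures are conditional on the listed assumptions. They run in both directions and do not show that the study is underpowered.

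This should be fixed. It affects how a non-significant result is read; it changes no test and no estimate.

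**What to change.** In section 4.4, remove the 95% power and reliability claim as it bears on the primary endpoints. If the t test was meant for eGFR, name eGFR as its endpoint and justify d = 0.5 with a standard deviation and time point.

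Then treat the roughly 120 stenosis patients as fixed. For each primary endpoint, state the hazard ratio detectable with 80% and with 95% power under the two-sided 5% log-rank test. This requires the matching ratio and the data cut-off to be written down, plus expected event numbers. Counts pooled over both groups are enough, so the comparison is not seen in advance.

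The cost is a rewording and a short calculation once the ratio and cut-off are chosen. No patients are added. The downside is a less favourable stated power.

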5. TREATMENT OF SUBJECTS

NA

5.1 Investigational product/treatment

<Please give a description of the intervention (medicinal product, medical device, food supplement, radiation, surgery, behavioural interventions, etcetera). Also use of comparator or placebo should be described.>

5.2 Use of co-intervention (if applicable)

< Please describe what subjects should do and not do (e.g. use co-medication, adequate contraception, diet). If it is allowed to use co-medication or other kind of intervention, it should be specified on forehand what is allowed.)>

5.3 Escape medication (if applicable)

<Please describe type, dose per unit and maximum dose allowed.>

6. INVESTIGATIONAL PRODUCT

NA

6.1 Name and description of investigational product(s)

6.2 Summary of findings from non-clinical studies

<One may refer to the Investigator's Brochure (IB), Investigational Medicinal Product Dossier (IMPD), Summary of Product Characteristics (SPC) or a similar document (if applicable), by mentioning the relevant pages in that document. Be sure that the information is up to date and references to peer reviewed papers in (biomedical/scientific) journals should be given where appropriate.>

6.3 Summary of findings from clinical studies

<See explanatory text of chapter 6.2, including remark>

6.4 Summary of known and potential risks and benefits

<See explanatory text of chapter 6.2, including remark>

6.5 Description and justification of route of administration and dosage

6.6 Dosages, dosage modifications and method of administration

6.7 Preparation and labelling of Investigational Medicinal Product

6.8 Drug accountability

<Please describe the procedures for the shipment, receipt, disposition, return and destruction of the investigational medicinal products.>

7. NON-INVESTIGATIONAL PRODUCT

NA

7.1 Name and description of non-investigational product(s)

7.2 Summary of findings from non-clinical studies

<One may refer to the Investigator's Brochure (IB), Investigational Medicinal Product Dossier (IMPD), Summary of Product Characteristics (SPC) or a similar document (if applicable), by mentioning the relevant pages in that document. Be sure that the information is up to date and references to peer reviewed papers in (biomedical/scientific) journals should be given where appropriate.>

7.3 Summary of findings from clinical studies

<See explanatory text of chapter 7.2, including remark>

7.4 Summary of known and potential risks and benefits

<See explanatory text of chapter 7.2, including remark>

7.5 Description and justification of route of administration and dosage

7.6 Dosages, dosage modifications and method of administration

7.7 Preparation and labelling of Non Investigational Medicinal Product

7.8 Drug accountability

<Please describe the procedures for the shipment, receipt, disposition, return and destruction of the non-investigational medicinal products.>

8. METHODS

8.1 Study parameters/endpoints

8.1.1 Main study parameter/endpoint

Primary outcome measures are patient survival and death-censored graft survival.

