3. STUDY DESIGN

This single-center retrospective study includes all kidney transplant patients who underwent kidney transplantation in Erasmus MC between 2010 and 2020. Data of patient characteristics, operation details and long-term outcomes will be collected. All patients will be divided into non-stenosis group and stenosis group based on the existence of pre-transplant aortoiliac stenosis. Propensity score matching will be used to make the baseline characteristics comparable between two groups. Patient survival, graft survival and long-term renal function of the two groups will be compared to indicate if the aortoiliac stenosis has an impact on the survival of transplant patients.

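### Do two unranked primary outcomes, each tested at p < 0.05, need a multiplicity rule or a stated decision rule?

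*Combined protocol and SAP*

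**What the plan says.** All references are to the combined protocol and SAP.

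- Section 8.1.1 (and the Summary): "Primary outcome measures are patient survival and death-censored graft survival". No order is given.
- Section 8.1.2: "Secondary outcome measures are renal function (such as eGFR) and vascular complications".
- Section 10: "Kaplan-Meier curves and log-rank test will be used to compare patient and graft survival", and "A p-value of < 0.05 is considered statistically significant". The threshold is general and is not divided between outcomes.
- Section 10.1 defines two time-to-event variables. For the first, "Patient survival is defined as the time from transplantation to death or the last follow-up". The second runs to graft failure and censors death with a functioning graft.
- Section 2 gives one primary objective: to assess the impact of pre-transplant stenosis on short- and long-term outcomes, in the plural.
- Section 3: "Patient survival, graft survival and long-term renal function of the two groups will be compared to indicate if the aortoiliac stenosis has an impact" on survival. This sentence puts both primary outcomes and a secondary one into a single question.
- Section 4.4: "Both the accepted false positive and negative rate is 5" per cent, for one two-sided t test with 105 patients per group.

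No section gives a hierarchy, an adjustment for multiplicity, or a rule for the case where one primary outcome is significant and the other is not.

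**The concern.** Two primary outcomes with one unsplit threshold are a familiar route to inflated type I error. The sentence in section 3 adds to the worry, because it reads as if several comparisons feed one verdict on whether stenosis has an impact.

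If so, a split result has no set interpretation. Read separately, the impact is on one outcome only. If either counts, there is an impact. If both are required, there is none.

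A split result is plausible. Death with a functioning graft is an event for patient survival and a censoring for graft survival, so stenosis could affect one outcome and not the other. In a retrospective study, leaving the rule open invites a choice after the results are known. An either-counts claim would also carry a false positive rate above the 5% named in section 4.4.

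**Working it through.** **1. The plan's own figure.** Inputs from section 4.4: two-sided t test, d = 0.5, alpha 0.05, n = 105 per group.

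- Noncentrality = d × √(n/2) = 0.5 × √52.5 = 3.6228
- Degrees of freedom = 2 × 105 − 2 = 208; critical t = 1.9714
- Power from the noncentral t distribution = 0.9501

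This matches the stated output. The 5% is the alpha of one test, so section 4.4 is not in error if each outcome is judged separately.

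**2. False positive rate under each reading.** Both nulls are taken as true, with two two-sided tests at 0.05. The test statistics are modelled as bivariate normal. The documents give no correlation ρ between them, so a range is assumed.

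- Either counts, ρ = 0: 1 − 0.95² = 0.0975
- Both required, ρ = 0: 0.05² = 0.0025
- In general: P(both) = 0.10 − P(either)

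| Reading | ρ = 0 | ρ = 0.2 | ρ = 0.6 | ρ = 0.9 |
|---|---|---|---|---|
| Separate, per outcome | 5% | 5% | 5% | 5% |
| Either counts | 9.75% | 9.6% | 8.8% | 7.0% |
| Both required | 0.25% | 0.36% | 1.25% | 2.96% |

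Only the either-counts row exceeds 5%.

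**3. How often the two tests would split.** P(exactly one significant) = P(either) − P(both). The power values are assumptions, because the plan gives no hazard ratio or event count.

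| Truth | ρ = 0 | ρ = 0.9 |
|---|---|---|
| Neither outcome affected | 2 × 0.05 × 0.95 = 9.5% | 4.1% |
| Both affected, power 95% each | 2 × 0.95 × 0.05 = 9.5% | 3.6% |
| Both affected, power 80% each | 2 × 0.80 × 0.20 = 32% | 10% |
| Both affected, power 50% each | 2 × 0.50 × 0.50 = 50% | 14% |
| One affected, power 50% | 0.95 × 0.50 + 0.05 × 0.50 = 50% | 50% |
| One affected, power 80% | 0.95 × 0.80 + 0.05 × 0.20 = 77% | 80% |
| One affected, power 95% | 0.95 × 0.95 + 0.05 × 0.05 = 90.5% | 94% |

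Splits are most common when stenosis truly affects one outcome only. In that case one significant and one non-significant result is usually the correct finding under the separate reading.

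**4. Which reading the text supports.**

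- Section 2: plural outcomes and no overall verdict. This favours separate questions, although the word for impact comes without a rule.
- Section 8.1.1: plural outcome measures. Favours separate questions.
- Section 10.1: two variables that treat death differently. Favours separate questions.
- Section 3: one pooled sentence that leans towards a combined claim. It also draws in renal function, which section 8.1.2 makes secondary. Taken literally, eGFR alone could then show an impact on survival, which no section proposes. It is better read as a loose summary of the design than as a decision rule.

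**5. What a clarification would change.** Stating the separate reading leaves the log-rank tests, the 0.05 threshold, the 105 per group and the data as they are.

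**The case for a change.** The best case for a change is that the separate reading is never stated and section 3 leans the other way, while a few words written before the results are known would settle the matter. When stenosis affects only one outcome, a split result occurs in half or more of studies at the assumed powers in step 3, so the question may well arise.

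The facts in this argument stand: the rule is missing, and the section 3 sentence does not match section 8.1.2. The consequence does not follow. The missing sentence would record the reading that sections 2, 8.1.1 and 10.1 already point to, and both results would be reported either way. Splits are also far less frequent in other plausible cases: about 4% to 10% when neither outcome is affected, or when both are with 95% power each.

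A formal procedure such as Holm would matter only if one either-counts claim were intended. The documents state no such claim, and this is a single-centre retrospective cohort with no stated confirmatory purpose, a setting in which statisticians differ on whether to adjust. Adjustment would also have a price. With alpha 0.025 on the plan's own t-test inputs, power falls from 95.0% to 91.3% at 105 per group. That figure only illustrates the cost, since a t-test power is not valid for the survival endpoints.

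**Conclusion.** No change is needed. The plan names two primary outcomes without ranking them or stating a decision rule. Its text is most naturally read as two separate questions, each with a 5% false positive rate, and that reading needs no split of alpha. A clarifying sentence in section 8.1.1, with the section 3 sentence reworded to match, would be an optional improvement in wording that alters no analysis or result.

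The possible inflation, to between 7.0% and 9.75% for assumed correlations of 0.9 down to 0, arises only if either outcome alone is taken to support one combined claim. The conclusion therefore rests on the separate reading. If the investigators did intend a single either-counts claim, a multiplicity rule would be needed.

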8.1.2 Secondary study parameters/endpoints (if applicable)

Secondary outcome measures are renal function (such as eGFR) and vascular complications.

8.1.3 Other study parameters (if applicable)

NA

8.2 Randomisation, blinding and treatment allocation

NA

8.3 Study procedures

Since this study is a retrospective study, no additional procedures/tests will be performed.

8.4 Withdrawal of individual subjects

Subjects can leave the study at any time for any reason if they wish to do so without any consequences. The investigator can decide to withdraw a subject from the study for urgent medical reasons.

8.4.1 Specific criteria for withdrawal (if applicable)

8.5 Replacement of individual subjects after withdrawal

8.6 Follow-up of subjects withdrawn from treatment

8.7 Premature termination of the study

< Please describe the criteria for terminating the study prematurely and the procedures in case the study will be terminated prematurely.>

9. SAFETY REPORTING

9.1 Temporary halt for reasons of subject safety

In accordance to section 10, subsection 4, of the WMO, the sponsor will suspend the study if there is sufficient ground that continuation of the study will jeopardise subject health or safety. The sponsor will notify the accredited METC without undue delay of a temporary halt including the reason for such an action. The study will be suspended pending a further positive decision by the accredited METC. The investigator will take care that all subjects are kept informed.

